4.2.2 Restrictions

4.2.2.1 Restrictions regarding concomitant treatment

The medications (or classes of medications) listed in [REDACTED] must not have been taken before [REDACTED] for the time periods as specified

Table 4.2.2.1: 1 Restricted medications

Medication or class of medications	Restriction duration
IL-36R inhibitors (other than spesolimab provided in the program)	4 weeks prior to any [REDACTED] and not until after 16 weeks after last [REDACTED] of spesolimab
Live vaccinations	
Anakinra (or other IL-1/IL-1R inhibitors)	Not to be administered concurrently with spesolimab

4.2.2.2 Restrictions on diet and lifestyle

No specific restrictions on diet or lifestyle of the patients are required.

4.2.2.3 Contraception requirements

Female patients:

WOCBP (for the definition please refer to section [3.2.3](#)) must use a highly effective method of birth control per ICH M3 (R2) that results in a low failure rate of less than 1% per year

Proprietary confidential information © 2022 Boehringer Ingelheim International GmbH or one or more of its affiliated companies

when used consistently and correctly during the study, and for a period of at least 16 weeks after the last dose of study drug.

Acceptable methods of birth control for this program are:

- Combined (estrogen and progestogen containing) hormonal birth control associated with inhibition of ovulation
- Progestogen-only hormonal birth control associated with inhibition of ovulation
- Intrauterine device (IUD) and intrauterine hormone-releasing system (IUS)
- Bilateral tubal occlusion (blocking of the fallopian tubes)
- Vasectomy of sexual partner (proven effective by absence of sperm in the ejaculate).
- Complete sexual abstinence (not to have male-female vaginal sex)

5. ASSESSMENTS

5.1 ASSESSMENT OF EFFICACY

[REDACTED]

5.2 ASSESSMENT OF SAFETY

Safety will be assessed descriptively based on the incidence of:

- Treatment emergent Adverse events (AEs)
- Treatment emergent Serious adverse events (SAEs)
- Treatment emergent Adverse events of special interest (AESIs).

No confirmatory safety analysis is planned.

5.2.1 Physical examination

A complete physical examination will be performed before first drug administration. Examination includes, at a minimum, general appearance, neck, lungs, cardiovascular system, abdomen, extremities, and skin. Measurement of height and body weight should also be performed.

Physical examination will be performed at follow-up visits according to standard clinical practice and when deemed appropriate by the treating physician.

The results must be included in the source documents available at the site.

5.2.2 Vital signs

Vital signs will be evaluated before first drug administration.

Vital signs will be evaluated at follow-up visits according to standard clinical practice and when deemed appropriate by the treating physician.

The results must be included in the source documents available at the site.

5.2.3 Safety laboratory parameters

Safety laboratory examinations include liver function tests for eligibility check: aspartate transaminase (AST/GOT), alanine transaminase (ALT/GPT), alkaline phosphatase, and total bilirubin.

Any additional laboratory testing during the program is optional and should be performed at the discretion of the treating physician in accordance with the current standard of care, which may yield useful information for the management and safety evaluation of the patient.

Clinically relevant abnormal findings as judged by the investigator will be reported as adverse events (please refer to section [5.2.4](#)).

In case the criteria for hepatic injury are fulfilled, a number of additional measures will be performed (please see section [5.2.4.1.4](#) and the DILI Checklist provided in the ISF).

5.2.4 Assessment of adverse events

5.2.4.1 Definitions of AEs

5.2.4.1.1 Adverse event

An AE is defined as any untoward medical occurrence in a patient or clinical investigation subject administered a medicinal product and which does not necessarily have to have a causal relationship with this treatment.

An AE can therefore be any unfavourable and unintended sign (including an abnormal laboratory finding), symptom, or disease temporally associated with the use of a medicinal product, whether or not considered related to the medicinal product.

The following should also be recorded as an AE in the CRF and BI SAE form (if applicable):

- Worsening of the underlying disease or of other pre-existing conditions
- Changes in vital signs, ECG, physical examination and laboratory test results, if they are judged clinically relevant by the investigator.

If such abnormalities already exist prior to program inclusion, they will be considered as baseline conditions and should be collected in the eCRF only.

5.2.4.1.2 Serious adverse event

A serious adverse event (SAE) is defined as any AE that fulfils at least one of the following criteria:

- results in death,
- is life-threatening, which refers to an event in which the patient was at risk of death at the time of the event; it does not refer to an event that hypothetically might have caused death if more severe,
- requires inpatient hospitalisation,
- requires prolongation of existing hospitalisation,

Proprietary confidential information © 2022 Boehringer Ingelheim International GmbH or one or more of its affiliated companies

- results in persistent or significant disability or incapacity,
- is a congenital anomaly / birth defect,
- is deemed serious for any other reason if it is an important medical event when based on appropriate medical judgement which may jeopardise the patient and may require medical or surgical intervention to prevent one of the other outcomes listed in the above definitions. Examples of such events are intensive treatment in an emergency room or at home for allergic bronchospasm, blood dyscrasias or convulsions that do not result in hospitalisation or development of dependency or abuse.

5.2.4.1.3 AEs considered “Always Serious”

In accordance with the European Medicines Agency initiative on Important Medical Events, Boehringer Ingelheim has set up a list of further AEs, which by their nature can always be considered to be “serious” even though they may not have met the criteria of an SAE as defined above.

The latest list of “Always Serious AEs” can be found in the eDC system. A copy of the latest list of “Always Serious AEs” will be provided upon request. These events should always be reported as SAEs as described above.

Cancers of new histology and exacerbations of existing cancer must be classified as a serious event regardless of the time since discontinuation of the drug and must be reported as described in [5.2.4.2](#), subsections “AE Collection” and “**AE reporting to sponsor and timelines**”.

5.2.4.1.4 Adverse events of special interest

The term adverse events of special interest (AESI) relates to any specific AE that has been identified at the project level as being of particular concern for prospective safety monitoring and safety assessment within this program, e.g. the potential for AEs based on knowledge from other compounds in the same class. AESIs need to be reported to the sponsor’s Pharmacovigilance Department within the same timeframe that applies to SAEs, please see section [5.2.4.2.2](#).

The following are considered as AESIs:

Potential Severe DILI

A potential severe DILI that requires follow-up is defined by the following alterations of hepatic laboratory parameters:

- an elevation of AST (aspartate transaminase) and/or ALT (alanine aminotransferase) ≥ 3 fold ULN combined with an elevation of total bilirubin ≥ 2 fold ULN measured in the same blood draw sample, or in samples drawn within 30 days of each other, or
- ALT, and/or AST elevations ≥ 10 fold ULN.

These lab findings constitute a hepatic injury alert and the patients showing these lab abnormalities need to be followed up according to the “DILI checklist” provided in the ISF. In case of clinical symptoms of hepatic injury (icterus, unexplained encephalopathy, unexplained coagulopathy, right upper quadrant abdominal pain, etc.) without lab results

Proprietary confidential information © 2022 Boehringer Ingelheim International GmbH or one or more of its affiliated companies

(ALT, AST, alkaline phosphatase, total bilirubin) available, the investigator should make sure these parameters are analysed. Should the results meet the criteria of hepatic injury alert, the procedures described in the DILI checklist should be followed.

Systemic hypersensitivity reactions including [REDACTED] reactions and anaphylactic reaction
Any suspicion of severe systemic hypersensitivity including [REDACTED] reactions and any anaphylactic reaction should be defined and assessed using the criteria discussed in the statement paper from Sampson et al. (Section [4.2.1.1](#) and Appendix [10.1, R11-4890](#)).

Severe infections (according to RCTC grading in the ISF)

Opportunistic and mycobacterium tuberculosis infections

These include pneumocystis jirovecii, BK virus disease including PVAN, CMV, posttransplant lymphoproliferative disorder (EBV), progressive multifocal leucoencephalopathy, bartonellosis (disseminated only), blastomycosis, toxoplasmosis, coccidioidomycosis, histoplasmosis, aspergillosis (invasive only), candidiasis (invasive or pharyngeal), cryptococcosis, other invasive fungi (mucormycosis (zygomycosis, rhizopus, mucor, lichtheimia), scedosporium/pseudallescheria boydii, fusarium), legionellosis, listeria monocytogenes (invasive only), tuberculosis, nocardiosis, non-tuberculous mycobacterium, salmonellosis (invasive only), HBV reactivation, herpes simplex (invasive only), herpes zoster, strongyloides (hyperinfection syndrome and disseminated forms only), paracoccidioides, penicillium marneffei, sporothrix schenckii, cryptosporidium species (chronic only), microsporidiosis, leishmaniasis (visceral only), trypanosoma cruzi infection (Chagas' disease) (disseminated only), campylobacteriosis (invasive only), shigellosis (invasive only), vibriosis (invasive due to vibrio vulnificus), HCV progression ([R17-2617](#)).

Peripheral neuropathy

Any event suspected or diagnosed as Peripheral Neuropathy is considered as an AESI. For the treatment interruption rules, please see section [1.4](#) and [3.2.4.1](#).

5.2.4.1.5 Intensity (severity) of AEs

The intensity (severity) of adverse events should be classified and recorded in the CRF according to the RCTC version 2.0 (refer to ICF for details).

5.2.4.1.6 Causal relationship of AEs

Medical judgement should be used to determine the relationship between the adverse event and the BI investigational compound, considering all relevant factors, including pattern of reaction, temporal relationship, de-challenge or re-challenge, confounding factors such as concomitant medication, concomitant diseases and relevant history.

Arguments that may suggest that there is a reasonable possibility of a causal relationship could be:

- The event is consistent with the known pharmacology of the drug.
- The event is known to be caused by or attributed to the drug class.
- A plausible time to onset of the event relative to the time of drug exposure.

- Evidence that the event is reproducible when the drug is re-introduced.
- No medically sound alternative aetiologies that could explain the event (e.g. pre-existing or concomitant diseases, or co-medications).
- The event is typically drug-related and infrequent in the general population not exposed to drugs (e.g. Stevens-Johnson syndrome).
- An indication of dose-response (i.e. greater effect size if the dose is increased, smaller effect size if dose is reduced).

Arguments that may suggest that there is no reasonable possibility of a causal relationship could be:

- No plausible time to onset of the event relative to the time of drug exposure is evident (e.g. pre-treatment cases, diagnosis of cancer or chronic disease within days / weeks of drug administration; an allergic reaction weeks after discontinuation of the drug concerned).
- Continuation of the event despite the withdrawal of the medication, taking into account the pharmacological properties of the compound (e.g. after 5 half-lives). Of note, this criterion may not be applicable to events whose time course is prolonged despite removing the original trigger.
- There is an alternative explanation, e.g. situations where other drugs or underlying diseases appear to provide a more likely explanation for the observed event than the drug concerned.
- Disappearance of the event even though the program drug treatment continues or remains unchanged.

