Systemic hypersensitivity reaction	After administration of any biologic agent or protein, there is a possibility of occurrence of immediate (such as anaphylaxis) or delayed (such as drug reaction with eosinophilia and systemic symptoms) adverse immune reactions.	Patients with a history of allergy/hypersensitivity to spesolimab or its excipients are excluded from the program. In case of systemic hypersensitivity reactions including anaphylactic reaction emerging during or after administration of spesolimab, the investigator should consider, in accordance with severity of the reaction and local standard of care, interruption of therapy and treatment of the condition. Systemic hypersensitivity reaction is defined as an AESI. It is subject to close monitoring and investigators are requested to assess these conditions using the criteria discussed in the statement paper from Sampson et al. [R11-4890].

Table 1.4: 1

Risks associated with spesolimab administration (cont.)

Risks of clinical relevance for this trial	Summary of data, rationale for the risk	Mitigation strategy
Infections	
Inhibition of the immune response with an immune-modulating biologic may increase the risk of infections.
 
In clinical trials with spesolimab, a higher proportion of patients with mild to moderate infections was seen in the spesolimab treatment group than in the placebo treatment group.
 
Nevertheless, there was no indication of an increased frequency of patients with severe, serious, and opportunistic infections in association with spesolimab treatment.
 
A recent characterisation of individuals with homozygous IL36R KO mutations revealed that normal immune function was broadly preserved, suggesting that IL36 signalling pathway inhibition may not substantially compromise host defenses [R17-3632].
	
Patients with any relevant chronic or acute infections including HIV, viral hepatitis or active tuberculosis are excluded from the trial. Treatment of infections should be initiated promptly according to standard of care.
 
Severe infections and opportunistic infections are considered AESI for this program. These conditions and serious infections are subject to close monitoring.

Table 1.4: 1

Risks associated with spesolimab administration (cont.)

Risks of clinical relevance for this trial	Summary of data, rationale for the risk	Mitigation strategy

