5.2.4.2 Adverse event collection and reporting

5.2.4.2.1 AE Collection

The investigator shall maintain and keep detailed records of all AEs in the patient files. The following must be collected and documented on the appropriate CRF(s) by the investigator:

- From signing the informed consent onwards until the individual patient's end of program (16 weeks after last dose of spesolimab, or at the time of withdrawal of participation): all AEs (serious and non-serious) and all AESIs.
- After the individual patient's end of program: the investigator does not need to actively monitor the patient for new AEs but should only report any occurrence of cancer and program drug-related SAEs and program drug-related AESIs of which the investigator may become aware of by any means of communication, e.g. phone call. Those AEs should however not be reported in the CRF.
- Upon patient re-entry into the program, the patient should be re-evaluated to ensure that eligibility criteria are still met and the overall program is still running in order to assess AEs (serious and non-serious) and AESIs.

Vital Status Data Collection

Patients who withdraw their consent to program participation, who agree to be contacted further but do not agree to physical visits, should be followed up as described in section [3.2.4.2](#), withdrawal from program treatment. Thus, for patients who withdraw their consent

but agree to be contacted by phone for a last follow-up assessment at 16 weeks after last drug intake, the investigator must report any occurrence of cancer, all deaths / fatal AEs regardless of relationship, and program drug-related SAEs and and program drug-related AESIs the investigator becomes aware of.

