7.1.1 Safety analyses

In general, safety analyses will be descriptive in nature and will be based on BI standards. No hypothesis testing is planned.

Adverse events will be coded using the Medical Dictionary for Drug Regulatory Activities (MedDRA). Standard BI summary tables and listings will be produced. Statistical analysis and reporting of adverse events will concentrate on treatment-emergent adverse events, i.e. all adverse events occurring between start of treatment and end of the REP, a period of 16 weeks after the last dose of program medication. Adverse events that start before first drug intake and deteriorate under treatment will also be considered as 'treatment-emergent'. All adverse events with an onset between start of treatment and end of the REP, a period of 16 weeks after the last dose of program medication, will be assigned to the on-treatment period for evaluation.

All treated patients will be included in the safety analysis.

Frequency, severity, and causal relationship of adverse events will be tabulated by system organ class and preferred term. after coding according to the current version of the Medical Dictionary for Drug Regulatory Activities (MedDRA) at database lock.

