The analyses of AEs will be descriptive in nature. All analyses of AEs will be based on the exposure adjusted incidence rates (per 100 patient years or per 100 flare treatment period years), as well as the number of patients with AEs and the number of flare treatment periods with AEs. System organ classes (SOCs) (if applicable) will be sorted according to the standard sort order specified by the European Medicines Agency (EMA), preferred terms (PTs) (if applicable) will be sorted by total frequency (within SOC).

For further details on summarization of AE data, please refer to "Handling and summarization of adverse event data for clinical trial reports and integrated summaries" ([3](#)) and "Handling of missing and incomplete AE dates" ([4](#)).

An overall summary of AEs will be described in all flare treatment period based on TS by per patient analysis. The exposure-adjusted incidence rate and frequency will be summarized by treatment, primary SOC and PT for the following AEs: drug-related AEs considered by the investigator, AEs leading to treatment discontinuation, other significant AEs, SAEs, drug-related SAEs, AESIs, and user-defined adverse event categories (UDAEC) and serious UDAEC (cf. [Table 7.8.1: 1](#)). AEs will also be summarized by the maximum intensity.

According to ICH E3 ([5](#)), the sponsor has defined AEs which are to be classified as ‘other significant’. For the current trial, these will include those non-serious AEs which were reported with ‘action taken = Drug Withdrawn’ or ‘action taken = Dose Reduced’.

The following are considered as AESIs (see Sec 5.2.4.1.4 of CTP):

- Potential Severe Drug Induced Liver Injury (DILI)
- Systemic hypersensitivity reactions including [REDACTED] reactions and anaphylactic reaction
- Severe infections (according to RCTC grading in the ISF)
- Opportunistic and mycobacterium tuberculosis infections
- Peripheral neuropathy

The investigator identified AESI will be captured from the eCRF and reported as “Investigator reported AESI” table. In addition, user defined adverse event concepts (UDAEC) identified through specific search criteria will be reported separately ([Table 7.8.1: 1](#)).

For disclosure of AE data on ClinicalTrials.gov, the frequency of subjects with non-serious AEs occurring with an incidence of greater than 5% (in preferred terms) will be summarized by treatment, primary system organ class and preferred term. The frequency of subjects with SAEs will also be summarized.

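### The causality guidance gives an allergic reaction weeks after stopping the drug as an unqualified example against relatedness, which may nudge delayed hypersensitivity towards a rating of not related

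*Protocol*

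**What the plan says.** Protocol 5.2.4.1.6 tells investigators how to judge relatedness. The governing sentence is "Medical judgement should be used to determine the relationship between the adverse event and the BI investigational compound, considering all relevant factors". Two lists follow. The list in favour of relatedness includes "A plausible time to onset of the event relative to the time of drug exposure". The list against opens with "Arguments that may suggest that there is no reasonable possibility of a causal relationship could be", and its first bullet, on onset times that are not plausible, gives as one example "an allergic reaction weeks after discontinuation of the drug concerned". The next bullet, on events that continue after withdrawal, is qualified by the pharmacology of the compound. The allergic-reaction example is not.

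Other parts of the protocol bear on the same events:

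- Table 1.4: 1 (Section 1.4) lists, under systemic hypersensitivity, the possibility of "delayed (such as drug reaction with eosinophilia and systemic symptoms) adverse immune reactions".
- Section 4.2.1.1 sets a separate laboratory and organ work-up for suspected delayed hypersensitivity.
- Section 7.1.1 counts events as treatment-emergent up to the "end of the REP, a period of 16 weeks after the last dose of program medication".
- Section 5.2.4.2.1 collects all AEs and AESIs until 16 weeks after the last dose or until withdrawal of participation. After that point the investigator "should only report any occurrence of cancer and program drug-related SAEs and program drug-related AESIs".

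SAP 7.8.1 tabulates "drug-related AEs considered by the investigator" and drug-related SAEs.

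**The concern.** The example reads like general guidance for continuously dosed drugs, where stopping treatment marks a clear break. Here each flare is treated with one administration and an optional second, so almost any reaction that is not immediate occurs after the drug has been stopped. Taken at face value, the example would count against relatedness for the delayed reactions that the protocol elsewhere asks investigators to look for.

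The program has no comparator (Protocol 4.1.1), so relatedness cannot be inferred from a difference between arms. The investigator's rating is the only attribution that the plan tabulates. For patients who leave early, it also decides whether some serious events are reported at all.

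**Working it through.** No sample size, power or event rate is involved. The check sets the passages side by side, with a small amount of arithmetic on the time windows.

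**1. The window.** Protocol 7.1.1 gives 16 weeks: 16 × 7 = 112 days. SAP Table 6.1: 1 ends the on-treatment period no later than 112 days after the last administration. The two agree.

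**2. How much of the window is weeks after the last dose.** The protocol does not define weeks, so a lower bound has to be assumed.

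- From day 7: (112 − 7)/112 = 105/112 = 93.75%.
- From day 14: (112 − 14)/112 = 98/112 = 87.5%.

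These are shares of calendar time only. They support the statement that most follow-up lies weeks after the last dose. They are not shares of reactions or of misrated events.

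**3. Does the example reach delayed reactions?** Section 5.2.4.1.6 says allergic, without a type or a time limit. Table 1.4: 1 puts immediate and delayed reactions under one heading. Section 4.2.1.1 treats them in separate paragraphs. Nothing in 5.2.4.1.6 tells the investigator which usage applies, so the example can be read as covering delayed hypersensitivity.

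**4. Which outputs depend on the rating?**

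| Output | Uses investigator causality? |
|---|---|
| Primary endpoint, TEAEs (Protocol 2.1.2) | No |
| Secondary endpoints, SAEs and AESIs (2.1.3) | No |
| AE collection while the patient is in the program (5.2.4.2.1) | No |
| Hypersensitivity and DRESS categories (SAP Table 7.8.1: 1) | No; MedDRA searches and a date-based algorithm |
| Drug-related AE and SAE tables (Protocol 7.1.1, SAP 7.8.1) | Yes |
| SUSAR classification, on which the notices in Protocol 8.6 rest | Yes; a SUSAR is a suspected reaction |
| Reporting after the individual end of program, including early withdrawal (5.2.4.2.1) | Yes |

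**5. The last row within the 16 weeks.** Withdrawal of participation ends the individual program early. From then on, only cancers and drug-related SAEs and AESIs are required, and these are not entered in the CRF. Deaths regardless of relationship are added for patients who withdraw consent but accept a telephone contact. A non-fatal serious delayed reaction at, say, week 5 in a patient who had already withdrawn is therefore reportable only if rated drug-related. Section 3.2.4.1 does ask for new AEs at a final contact at 16 weeks, but only where possible. For the specific information to be collected, it refers back to 5.2.4.2.1.

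**6. Size.** The documents give no half-life, no rate of delayed reactions and no rate of misattribution. The number of events affected cannot be computed.

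**The case against.** The case on the other side is substantial.

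- **The text is permissive.** It is one example in a list of arguments that may count against relatedness. Medical judgement on all factors governs, and plausible onset is listed as an argument in favour. This stands. A reader might infer that drug-related reactions will be under-attributed, but the documents support only that they may be. The section as a whole points both ways; it is the example alone that can push in only one direction.
- **The residual effect period is not a causality standard.** It assigns events to the on-treatment period, and treatment-emergent and drug-related are different concepts. This stands. A reader might see a formal contradiction between 5.2.4.1.6 and 7.1.1; there is none. Nor does any section say that delayed reactions are expected throughout the 16 weeks.
- **Allergic may mean immediate-type.** Section 4.2.1.1 uses the word that way: its example of a severe allergic reaction is anaphylaxis, and sampling starts at half an hour. This reading is fair, but 5.2.4.1.6 does not state it, and one added word would settle the matter.
- **The earlier DRESS reports do not show late onset.** In Section 1.2.3 the only timing given is two days after treatment in one case. RegiSCAR scores were 3 or lower, and both patients had received paracetamol and antibiotics. This stands: the reports make the event type relevant and say nothing about onset weeks later.
- **Most consequences are contained.** For patients still in the program, every AE is collected, and SAEs and AESIs reach the sponsor within 24 hours (5.2.4.2.2). This stands. It does not follow that causality-dependent reporting begins only after 16 weeks, because early withdrawal brings it forward.

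**Conclusion.** The point holds as a wording weakness. An example with no limit on type or time fits poorly with a product given once or twice per flare and with the protocol's own attention to delayed hypersensitivity. It may move some delayed reactions towards a rating of not related.

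The reach is narrow: the drug-related AE and SAE tables, SUSAR classification, and non-fatal SAEs and AESIs other than cancer in patients who withdraw before 16 weeks. The primary and secondary endpoints and the MedDRA-search categories do not change, and no hypothesis is tested.

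The 87.5% to 93.75% in the working might be taken as the share of reactions at risk of misrating. It is a share of days under an assumed meaning of weeks.

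The conclusion rests on two assumptions: that some investigators would read allergic as including delayed hypersensitivity, and that a listed example carries some weight in their judgement. The documents neither confirm nor exclude either one.

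**What to change.** Reconcile Protocol 5.2.4.1.6 with Table 1.4: 1, Section 4.2.1.1 and Section 7.1.1:

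1. Delete the allergic-reaction example, or limit it to immediate-type allergic reactions.
2. Add a sentence that onset of a hypersensitivity reaction within the 16-week residual effect period is not by itself an argument against relatedness.

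The added sentence should not declare every onset within 16 weeks plausible for all event types. That would turn an analysis window into a presumption of causality. It would also clash with the same bullet, which treats a cancer diagnosed within days or weeks of administration as an implausible onset.

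The cost is one or two sentences in the protocol and a note to sites. No analysis program changes. The downside is that a few more hypersensitivity events may be rated drug-related.
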